#### 5.3.3 *Patient Global Impression-Improvement (PGI-I)*

The PGI-I was selected for the ability to obtain patient impressions of improvement in overall functioning. The PGI-I will be completed at the 2 week, 4 week, 8 week, and 12 week visits. Secondary outcome measures will include the proportion “much improved” or “very much improved” on PGI-I at 12 weeks. Participants will be trained to complete this scale by the study coordinator at the screening visit and the study coordinator will review the scale for completion.

#### 5.3.4 *Hamilton Anxiety Rating Scale (HAM-A)*

Despite concerns about construct validity and predictive validity, the 14-item HAM-A was selected because it is a widely used clinician-rated measure and has demonstrated sensitivity to change. The HAM-A will be administered by an investigator at baseline and each subsequent telephone and in-person study visit. There is precedent for administering the HAM-A by telephone and it was done in a study of telephone-based cognitive behavioral therapy for depression in PD. Secondary outcome measures will include the mean change in HAM-A from baseline to 12 weeks and proportion of responders (>50% reduction from baseline or reduction to  $\leq 7$  in HAM-A).

#### 5.3.5 *Hospital Anxiety and Depression Scale (HADS)*

Although there are some concerns regarding validity in the PD population, the HADS was selected because it is a self-rated measure with anxiety and depression subscales and multiple studies have shown acceptable psychometric properties in the PD population. This 14-item self-rated scale does not include somatic symptom questions, which could potentially overlap with PD symptoms. It will be completed at baseline and each subsequent in-person study visit. Secondary outcome measures will include mean change in HADS from baseline to 12 weeks. Participants will be trained to complete this scale by the study coordinator at the screening visit and the study coordinator will review the scale for completion.

#### 5.3.6 *Unified Dyskinesia Rating Scale (UDysRS)*

The UDysRS was selected as it is a comprehensive, PD-specific tool that incorporates both historical and objective data. It has been shown to be superior to multiple other dyskinesia rating scales. It will be administered by an investigator at baseline and each subsequent in-person study visit. Investigators will have completed the certification course to ensure adequate inter-rater reliability. In order to minimize

differences in scores attributable to the timing of Parkinson's disease medications, investigators will always attempt to administer the UDysRS during the ON state (generally about 1 hour after levodopa administration). Secondary outcome measures will include mean change in UDysRS from baseline to 12 weeks.

## 5.4 Safety Assessments

### 5.4.1 Medical Assessment

A general medical examination will be performed by an investigator at the screening visit. The need for liver function tests, BUN and creatinine to determine the presence of significant renal or liver impairment at screening or to evaluate an adverse event will be left to the discretion of the investigator. The investigator may decide such testing is indicated based on the reporting of a history of certain medical conditions or surgeries, the presence of symptoms that may indicate renal or liver impairment, or examination findings that are concerning for renal or liver impairment. A serum pregnancy test will be obtained at screening for all women of child-bearing potential. All blood and urine tests will be obtained on-site and sent to URMC Labs for processing. A complete list of concomitant medications will be obtained at screening, baseline, and all subsequent telephone and in-person study visits by a study coordinator. A medical health update will be obtained by a study coordinator at baseline and all subsequent telephone and in-person study visits.

### 5.4.2 Confirmation of Diagnosis of Parkinson's Disease

The diagnosis of PD will be confirmed by an investigator following a complete neurological examination using the UK Parkinson's Disease Society Brain Bank Clinical Diagnostic Criteria at the screening visit. The NINDS Common Data Elements Parkinson's Disease Medical History form will be completed by an investigator to better characterize the participants Parkinson's disease at the baseline visit.

### 5.4.3 Montreal Cognitive Assessment (MOCA)

The MOCA is a reliable and valid instrument in Parkinson's disease and is felt to be a better screening instrument in Parkinson's disease than the commonly used Mini-Mental State Exam (MMSE). It will be administered by an investigator at the screening visit and significant cognitive impairment will be defined as a score < 23.

### 5.4.5 Movement Disorders Society-Unified Parkinson's Disease Rating Scale (MDS-UPDRS)

The MDS-UPDRS has been previously validated, is increasingly being used in Parkinson's disease clinical trials, and is preferable over the UPDRS due to its ability to more finely discriminate degree of impairment. The minimally clinically important difference for improvement (-3.25) and worsening (4.63) on the MDS-UPDRS Motor was recently established. Investigators will be required to provide verification of their completion of the MDS-UPDRS certification course to ensure adequate inter-rater reliability. In order to minimize differences in scores attributable to the timing of Parkinson's disease medications, for participants who are on levodopa investigators will always attempt to administer the MDS-UPDRS Motor during the ON state (generally about 1 hour after levodopa administration). MDS-UPDRS Item 2.3 *Chewing and Swallowing* will be completed by the participant at the screening visit to screen for dysphagia that may result in difficulty swallowing the study drug and would preclude safe participation in the study. A score of  $\geq 2$  ("I need to have my pills cut or

my food specially prepared because of chewing or swallowing problems, but I have not choked over the past week”) will exclude the participant from the study. The full MDS-UPDRS, including Part 1: Non-Motor Aspects of Experiences of Daily Living, Part II: Motor Aspects of Experiences of Daily Living, Part III: Motor Examination, and Part IV: Motor Complications, will be administered by an investigator at the baseline visit and the participant will complete those aspects of the MDS-UPDRS covered in the patient questionnaire (items 1.7-1.13 and 2.1-2.13). The MDS-UPDRS Motor will be administered by an investigator at each subsequent in-person study visit.

#### 5.4.6 *Vital Signs*

Pulse, temperature, weight, and blood pressure will be obtained at every in-person study visit.

#### 5.4.7 *Adverse Events*

Soliciting of adverse events will be non-specific and participants will be asked the question, “Do you feel different in any way since starting the new treatment?” All adverse events occurring after the baseline visit will be reported. All subsequent adverse events will be reported regardless of relationship to drug.

At each in-person and telephone visit, a study coordinator will solicit adverse events. Adverse events not previously documented in the study will be recorded in the adverse event section in the case report form. The nature of each individual event, date and time of onset, duration, severity, and relationship to treatment will be established by the investigator. Likely alternative etiologies should be recorded for events considered unrelated to study drug. Details of change to the dosing schedule, any corrective treatment, or prescription of a concomitant medication, must be recorded on the appropriate pages of the case report form. We will use the UKU Side Effects Rating Scale, developed by the Committee on Clinical Investigations (Udvalg for kliniske undersøgelser, UKU), which is a standing committee under the Scandinavian Society of Psychopharmacology. Items in the UKU are sub-grouped into psychic, neurological, autonomic, and other categories. The cardinal PD symptoms of tremor, rigidity, and hypokinesia are included.

Adverse events already documented in the CRF, at a previous visit, and designated as ‘continuing’ should be reviewed at each visit. If an adverse event is resolved, the documentation in the CRF must be completed to that effect. If an adverse event changes in frequency or severity during a study period, a NEW record of that event will be initiated. A record of all adverse events will be reviewed periodically by the study investigators. The documentation and classification of adverse events is further reviewed in section 9.

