## 5.2 **Timing of Visits**

### 5.2.1 *Screening Visit*

The screening visit will occur within 0-14 days of the baseline visit. Prior to completing any study activities, written informed consent will be obtained. Participants will be assigned a confidential participant identification number. The study coordinator and investigator will assess potential participants for study eligibility. All of the inclusion criteria and none of the exclusion criteria must be met. If a participant is being withdrawn from a medication to qualify for the study, the consent form must be signed prior to the initiation of the withdrawal.

Evaluations:

- Informed Consent
- Neurological Examination
- General Medical Examination
- Past Medical History
- Concomitant Medications
- Labs (if required as determined by investigator)
- Verification of Parkinson's disease diagnosis (UK Brain Bank Criteria)
- MOCA
- Vital Signs
- Parkinson Anxiety Scale
- MDS-UPDRS Item 2.3
- Urine pregnancy test for women of child-bearing potential

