### 5.2.2 *Baseline Visit*

The baseline visit will occur within 0-14 days of the screening visit. If laboratory studies are obtained at the screening visit, results must be reviewed prior to the baseline visit. Participants will be randomized to one of two treatment groups. Participants will be randomized to group according to a computer-generated randomization scheme. Based on this randomization, study personnel will be informed which drug bottles to supply the participant. The first dose of study drug or placebo should be taken the following morning.

Evaluations:

- Demographics
- Health Update
- Concomitant Medications
- NINDS Common Data Elements PD Medical History
- MDS-UPDRS
- Vital Signs
- Unified Dyskinesia Rating Scale
- Parkinson Anxiety Scale
- Hamilton Anxiety Scale

- Hospital Anxiety and Depression Scale

**5.2.3 Visit 01 (Day 14 +/- 3 days), Visit 02 (Day 28 +/- 3 days), Visit 03 (Day 56 +/- 3 days), and Visit 04 (Day 84 +/- 3 days)**

Visit 01, Visit 02, Visit 03, and Visit 04 should occur within 3 days of the target date. Previously dispensed study drug bottles will be collected and new study drug bottles dispensed at each visit.

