**Evaluations:**

- Health Update
- Concomitant Medications
- Adverse Events
- UKU Side Effect Rating Scale
- MDS-UPDRS Motor Component
- Vital Signs
- Unified Dyskinesia Rating Scale
- Parkinson Anxiety Scale (except at Visit 01)
- CGI-Improvement
- PGI-Improvement
- Hamilton Anxiety Rating Scale
- Hospital Anxiety and Depression Scale
- Dosage Assessment
- Adherence Assessment

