### 9.1 Adverse Event Definition

An adverse event is any symptom, sign, illness, or event which develops or worsens during the course of the study, whether or not the event is considered related to study drug.

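### The UKU side-effect scale is rated at every post-baseline visit but never before the first dose, so its items cannot be read as change from baseline

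*Combined protocol and SAP*

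**What the plan says.** Section 5.4.7 describes two ways of collecting side effects: an open question about feeling different since treatment began, and the UKU. On the UKU's content it says "Items in the UKU are sub-grouped into psychic, neurological, autonomic, and other categories" and adds "The cardinal PD symptoms of tremor, rigidity, and hypokinesia are included".

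The evaluation list for Visits 01 to 04 (5.2.3) contains the "UKU Side Effect Rating Scale", as do the lists for the telephone visits (5.2.4), unscheduled visits (5.2.5) and the premature termination visit (5.2.6). The lists for screening (5.2.1) and baseline (5.2.2) do not. Section 5.2.2 fixes the start of treatment after the baseline visit: "The first dose of study drug or placebo should be taken the following morning".

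Section 9.1 limits adverse events to what "develops or worsens during the course of the study". The number and type of adverse events is a secondary outcome in the synopsis, and section 13.2 tabulates adverse events by treatment group and severity, with 95% intervals for incidence. Section 13.2 does not name the UKU.

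**The concern.** The trial's objective is tolerability, and the UKU is the one instrument that goes through side effects item by item. Every participant enters with PD and clinically significant anxiety, and section 6.1 permits stable antidepressants, anxiolytics and antipsychotics. Some items may well be positive before the first capsule. With no pre-treatment rating, a positive item at week 2 could be old or new, and a worsened item looks the same as an unchanged one.

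Adverse event judgements have consequences. They are a secondary outcome. They bear on whether the dosage is raised, held or reduced (5.1.2, 8.2). They also separate failures due to adverse events from other failures in the secondary analysis in 13.2. Section 5.4.7 does not say how a symptom already present should be handled when the UKU is scored.

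**Working it through.** **1. When the UKU is given.** The schedule of activities has 11 columns. The UKU row is blank in all 3 pre-treatment columns (Screening, Baseline, Entry) and marked in the other 8: weeks 2, 4, 6 (phone), 8, 10 (phone) and 12, the adverse event visit and the premature termination visit. The lists in 5.2.1 to 5.2.6 agree, so the finding does not depend on how the table was extracted. There are 0 pre-treatment ratings against 6 routine on-treatment ratings, and no change score can be formed for any item.

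**2. Which symptoms have a matched measure before and during treatment.**

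| Domain | Before first dose | On treatment | Matched? |
|---|---|---|---|
| Motor signs | Full MDS-UPDRS at baseline | MDS-UPDRS motor at weeks 2, 4, 8, 12 | Yes, but not at the telephone visits |
| Anxiety | HAM-A, HADS, PAS | HAM-A at every visit; HADS at in-person visits; PAS at weeks 4, 8, 12 | Yes |
| Depressive symptoms | HADS | HADS at in-person visits | Yes |
| Dyskinesia | UDysRS | UDysRS at in-person visits | Yes |
| Other psychic, autonomic and other items | History, examination and MDS-UPDRS Parts I, II and IV | UKU only | No |

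Section 5.4.5 says that the full MDS-UPDRS "will be administered by an investigator at the baseline visit and the participant will complete those aspects of the MDS-UPDRS covered in the patient questionnaire", but only the motor part is repeated later. Section 5.3.5 notes that the HADS leaves out somatic symptoms. At weeks 6 and 10 a dosage assessment is made with the UKU and HAM-A but without MDS-UPDRS motor.

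**3. Where the expected side effects fall.** Sections 2.2 and 13.1 name headache, nausea, drowsiness, dizziness and motor worsening as the expected intolerabilities. Only the last has a matched repeated scale. The protocol does not list the UKU items, so it is an assumption that the other four lie within the psychic, neurological, autonomic and other groups.

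**4. Whether placebo can supply the reference.** The design size gives 27 − 21 = 6 on placebo. If all 35 were randomised 4:1 there would be 35 × 0.2 = 7 (section 3.1 says the 35 include screen failures, so 7 is an upper figure).

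- Exact (Clopper-Pearson) 95% intervals: 0 of 6, 0% to 46%; 3 of 6, 12% to 88%; 3 of 7, 10% to 82%.
- Approximate 95% half-width for the difference between arms, 1.96 × √[p(1−p)(1/n₁ + 1/n₂)], at an assumed item rate p = 0.5 in both arms: 21 v 6, 1.96 × √(0.25/21 + 0.25/6) = 0.454; 28 v 7, 1.96 × √(0.25/28 + 0.25/7) = 0.414.
- At an assumed p = 0.12, the highest side-effect rate quoted in section 1.3 (dizziness): 21 v 6, 1.96 × √(0.1056 × 0.2143) = 0.295; 28 v 7, 1.96 × √(0.1056 × 0.1786) = 0.269. The normal approximation is rough with so few on placebo.

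The half-width is therefore about 27 to 45 points, against quoted rates of 6% to 12% for the four side effects above. Section 2.4 itself says the study is not powered for comparing the groups.

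**The case against.** The strongest reply is that the trial does not rely on the UKU. Section 9 assigns the monitoring of motor worsening to MDS-UPDRS motor, and 13.2 analyses its change from baseline. Anxiety has three repeated scales. The open question itself asks about change since starting treatment. Investigators record onset, alternative causes and relationship on a five-level scale, with history, examinations and a baseline health update available to them. The primary outcome does not use the UKU, and no planned analysis names it.

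Most of this stands, and it rules out stronger readings. A reader might infer that PD and anxiety symptoms present at entry cannot be told apart from drug effects. The documents do not support that: the motor signs in the sentence quoted from 5.4.7 are among the best-covered symptoms. A reader might also infer that each positive UKU item becomes an adverse event; nothing in 5.4.7 or 9.3 says so. Nor is there ground for inferring that the primary tolerability result is biased.

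The reply does not reach the remaining items. A medical history and an open question are not itemised severity ratings, and they cannot show whether a given UKU item rose. Absence from 13.2 limits the harm, but it also leaves a scale collected six times per completer with neither a reference value nor a stated use.

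**Conclusion.** The point holds in limited form. UKU items cannot be read as change from baseline or checked against the definition in 9.1. Matched measures cover motor, anxiety and depressive symptoms, with no motor scale at the two telephone visits. Most other psychic, autonomic and other items have none, and the placebo arm is too small to replace one.

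The effect is limited to UKU ratings and the adverse event recording they inform; its size on adverse event counts cannot be estimated from the documents. The scheduling fact is certain. The practical weight rests on two assumptions: that the expected non-motor side effects are UKU items, and that some participants have them before treatment. This is a cheap improvement, not a flaw in the main conclusion.

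**What to change.** Add the UKU to the evaluations in 5.2.2 and to the Baseline column of the schedule, completed before the first dose. A participant's pre-treatment rating cannot be recovered once dosing starts.

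In 13.2, add a descriptive table by arm of the number of participants with each UKU item above its baseline score while on study drug, at any visit and visit by visit. The any-visit count sets the worst of up to six ratings against a single baseline, so rating noise alone will push it up; the visit-by-visit columns guard against over-reading it. No test is needed.

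In 5.4.7, say that the baseline UKU informs, but does not decide, whether a symptom is new or worsened under 9.1. The same edit could reconcile the start of adverse event reporting, which is after the baseline visit in 5.4.7 and from consent in 9.3.

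The cost is a slightly longer baseline visit and one table. Staff already give the scale at every later visit.

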### 5.5 **Assessment of Participant Compliance**

In order to determine adherence, participants will be asked to complete an adherence questionnaire in conjunction with the study coordinator and will be instructed to bring previously dispensed study drug bottles to each in-person visit and following telephone visits for pill counts. Pill counts will be performed by the study coordinator and the results recorded on a standard data form to monitor participant adherence. At the end of the study, all returned study medication will be counted and compared to the data

form. Any discrepancies will be resolved and the data form will be updated as necessary.

## **5.6 Dosage Assessment**

At each visit, the investigator will consider the need for dosage adjustment. If a dosage is tolerable, the investigator will increase the dosage if optimal anxiolytic effect (defined as Hamilton Anxiety Scale score <50% of baseline score or  $\leq 7$ ) has not been attained. This is further detailed in section 5.1.2.

## **5.7 Costs to the Participant**

Neither the participant nor the participant's insurance will incur any costs as a result of participation in this study.

## **5.8 Payment for Participation**

Participants will not be paid. Participants will be reimbursed at a rate of \$0.54/mile for travel by car. Participants will be reimbursed up to \$50 per study visit for travel expenses.

## **5.9 Return of Individual Research Results**

Research results will not be provided to the participant. The exception will be results of laboratory studies, which may be obtained at the discretion of an investigator. Incidental findings that might have health consequences for the participant will be communicated to the participant and his/her primary care provider.

## **5.10 Pregnancy and Nursing**

Female participants of childbearing potential will be advised to use adequate birth control as there is insufficient data regarding the effects of buspirone on the fetus. Adequate birth control methods include surgical sterilization, a partner who has had a vasectomy, oral contraceptives, condom plus spermicidal cream/jelly, cervical cap plus spermicidal cream/jelly, diaphragm plus spermicidal cream/jelly, intrauterine device (in place for at least 3 months) plus spermicidal cream/jelly, or contraceptive implant or injection. Abstinence is considered an acceptable contraceptive regimen.

If a participant becomes pregnant during the study, it is important that they notify a study team member immediately. In such an event, the study drug must be tapered immediately. The participant may continue in the study off of study drug. All attempts will be made to follow the participant until delivery.

## **6.0 CONCOMITANT AND DISALLOWED MEDICATIONS**

### **6.1 Allowed Concomitant Medications**

Enrolling participants may be on PD medications, with the exception of monoamine oxidase inhibitors. The dosage must be stable for 30 days prior to the baseline visit.

No new PD medications may be initiated for the duration of the study and no increases in the dosages of current PD medications will be allowed.

Enrolling participants may be on antidepressants (with the exception of monoamine oxidase inhibitors), antipsychotics, and/or anxiolytics. The dosage must be stable for 30 days prior to the baseline visit and for the duration of the study. The initiation of one of these medications will be prohibited for the duration of the study.

Strong CYP3A4 inhibitors (atazanavir, boceprevir, ceritinib, clarithromycin, cobicistat and cobicistat containing formulations, darunavir, idelalisib, indinavir, itraconazole, ketoconazole, lopinavir, nefazodone, nelfinavir, ombitasvir-paritaprevir-ritonavir, ombitasvir-paritaprevir-ritonavir plus dasabuvir, posaconazole, ritonavir and ritonavir containing formulations, saquinavir, telaprevir, telithromycin, and voriconazole) will be allowed. Participants will be monitored for potential adverse events related to an increase in the serum study drug concentration.

Strong CYP3A4 Inducers (carbamazepine, enzalutamide, fosphenytoin, lumacaftor, mitotaine, phenobarbital, phenytoin, primidone, rifabutin, rifampin, and rifapentine) will be allowed.

Non-dihydropyridine calcium channel blockers (diltiazem, verapamil) and interacting macrolide antibiotics (erythromycin, clarithromycin, and telithromycin) will be allowed. Participants will be monitored for potential adverse events related to an increase in the serum study drug concentration.

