### 5.1.2. Dosage Adjustments

Study investigators and study team members, with the exception of the study team member managing drug dispensation, will be blinded to treatment assignment. To minimize the risk for investigator bias influencing dosage adjustments we will employ specific parameters for dosage adjustment. If a dosage is tolerable, the investigator will increase the dosage if optimal anxiolytic effect (defined as Hamilton Anxiety Scale score <50% of baseline score or  $\leq 7$ ) has not been attained. Participants will not be blinded to dosage adjustments but will remain blinded to treatment assignment. Pre-specified dosage levels of 7.5 mg twice daily, 10 mg twice daily, 15 mg twice daily (with 3 preceding days of 12.5 mg twice daily), 20 mg twice daily (with 3 preceding days of 17.5 mg twice daily), 25 mg twice daily (with 3 preceding days of 22.5 mg twice daily), and 30 mg twice daily (with 3 preceding days of 27.5 mg twice daily) will be imposed as detailed in the following table. The investigator will be allowed to decrease the dosage or not escalate the dosage if there are adverse events.

REGIMEN DESCRIPTION				
Agent	Precautions	Dose	Route	Schedule
Buspirone	Take consistently either with or without food.	7.5 mg twice daily	Oral	Week 1-2
Placebo	Take consistently either with or without food.	7.5 mg twice daily	Oral	Week 1-2

DOSAGE ADJUSTMENTS					
Agent	Precautions	Prior Dose	New Dose	Route	Schedule
Buspirone	Take consistently either with or without food.	7.5 mg twice daily	10 mg twice daily	Oral	Week 1-2
		10 mg twice daily	15 mg twice daily	Oral	Day 1-3: 12.5 mg twice daily Day 4-14: 15 mg twice daily
		15 mg twice daily	20 mg twice daily	Oral	Day 1-3: 17.5 mg twice daily Day 4-14: 20 mg twice daily
		20 mg twice daily	25 mg twice daily	Oral	Day 1-3: 22.5 mg twice daily Day 4-14: 25 mg twice daily
		25 mg twice daily	30 mg twice daily	Oral	Day 1-3: 27.5 mg twice daily Day 4-14: 30 mg twice daily
Placebo	Take consistently either with or without food. Avoid grapefruit.	7.5 mg twice daily	10 mg twice daily	Oral	Week 1-2
		10 mg twice daily	15 mg twice daily	Oral	Day 1-3: 12.5 mg twice daily Day 4-14: 15 mg twice daily
		15 mg twice daily	20 mg twice daily	Oral	Day 1-3: 17.5 mg twice daily Day 4-14: 20 mg twice daily
		20 mg twice daily	25 mg twice daily	Oral	Day 1-3: 22.5 mg twice daily Day 4-14: 25 mg twice daily

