## 6.2 Disallowed Medications and Supplements

The following medications will not be allowed during the study:

- Selective and non-selective MAO inhibitors including those whose primary mechanism of action is not monoamine oxidase inhibition: phenelzine, rasagiline, selegiline, procarbazine, isocarboxazid, tedizolid, tranylcypromine, syrian rue, linezolid, methylene blue, moclobemide
- Initiation of any antidepressants, antipsychotics, or anxiolytics.
- Azelastine
- Conivaptan
- Dapoxetine
- Fusidic Acid
- Idelasib
- Orphenadrine
- Paraldehyde
- Thalidomide
- Grapefruit juice, ginkgo biloba, St. John's wort, and ginseng (which interfere with study drug metabolism).
- Initiation of any new PD medications and increases in the dosage of existing PD medications will be prohibited.
- Participants will also be prohibited from beginning any form of psychotherapy following study entry.

If treatment with a disallowed medication is required, the study drug should be discontinued and the participant should continue in the study off of the study drug. The study drug may be restarted after the disallowed medication is stopped.

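### Starting a CYP3A4 inhibitor or stopping an inducer after titration triggers no dosing hold and no express option to reduce pre-emptively, and idelalisib is allowed in 6.1 but apparently disallowed in 6.2

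*Combined protocol and SAP*

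**What the plan says.** Section 1.3 states that buspirone is metabolised through CYP3A4. Section 6.1 then deals with three groups of interacting drugs:

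- Strong CYP3A4 inhibitors are allowed, with the provision "Participants will be monitored for potential adverse events related to an increase in the serum study drug concentration".
- "Non-dihydropyridine calcium channel blockers (diltiazem, verapamil) and interacting macrolide antibiotics (erythromycin, clarithromycin, and telithromycin) will be allowed", followed by the same monitoring sentence.
- "Strong CYP3A4 Inducers (carbamazepine, enzalutamide, fosphenytoin, lumacaftor, mitotaine, phenobarbital, phenytoin, primidone, rifabutin, rifampin, and rifapentine) will be allowed". The paragraph ends there.

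The 30-day stability and no-initiation rules in 6.1 and 6.2 cover PD drugs and antidepressants, antipsychotics and anxiolytics. They do not cover inhibitors or inducers as a class. Nefazodone, an antidepressant on the inhibitor list, is the exception: starting it is already prohibited.

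On dosing, 5.6 says "If a dosage is tolerable, the investigator will increase the dosage if optimal anxiolytic effect" has not been reached, and 5.1.2 says the same. Section 5.1.2 adds "The investigator will be allowed to decrease the dosage or not escalate the dosage if there are adverse events", which 8.2 repeats.

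The allowed inhibitors in 6.1 include "darunavir, idelalisib, indinavir, itraconazole, ketoconazole". The disallowed list in 6.2 contains Idelasib. If a disallowed drug is needed, "the study drug should be discontinued and the participant should continue in the study off of the study drug".

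**The concern.** The protocol recognises that study drug concentration may rise and responds with monitoring alone. The written escalation rule looks only at HAM-A and tolerability. A participant who has just started a strong inhibitor and has no symptoms yet therefore meets the rule for a further increase. Stopping an inducer acts in the same direction, and there not even monitoring is mentioned.

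Motor worsening is the main PD-specific tolerability concern (2.2). Section 10.1 takes reassurance from the two largest earlier studies, where worsening occurred only above 60 mg/day, a dosage this trial will not use. A cap on dosage does not cap exposure once an inhibitor is added. The plan also treats a weaker case more strictly: "Grapefruit juice, ginkgo biloba" and two other herbal products are barred in 6.2 because they interfere with study drug metabolism.

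On idelalisib, staff cannot tell whether study drug must be stopped. A stop that is not reversed counts as intolerability under 13.2.

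**Working it through.** **Plan's own figures.** None bears directly on this point. For context, the primary rule (7 or more failures among 21) reproduces: exact binomial power at a 40% rate is 0.7998, and 21/0.8 = 26.25 rounds up to 27. Nothing below disturbs that count.

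**Fastest titration (5.1.2 levels, nominal days).** In mg/day: days 1-14, 15; 15-28, 20; 29-31, 25; 32-42, 30; 43-45, 35; 46-56, 40; 57-59, 45; 60-70, 50; 71-73, 55; 74-84, 60. The maximum is held for 84 - 74 + 1 = 11 days.

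**Illustrative exposure.** The documents give no fold-change f, so 1.5, 2, 3 and 4 are assumed. A day counts when dosage x f > 60, that is, when dosage > 60/f.

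| f | 60/f | Qualifying days | Upper bound |
|---|---|---|---|
| 1.5 | 40 | 57-84 | 28 |
| 2 | 30 | 43-84 | 42 |
| 3 | 20 | 29-84 | 56 |
| 4 | 15 | 15-84 | 70 |

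These bounds need escalation at every review and the interaction present throughout the qualifying days. Shorter overlap gives less:

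- Interaction from day 43 to day 84: 28 days at f = 1.5, 42 days at f = 2 to 4.
- From day 57: 28 days. From day 71: 14. From day 74: 11 (all f).
- A 7-day course from day 43: 0 days at f = 1.5 (40 x 1.5 = 60, not above), 7 days at f = 2 to 4. From day 57 or 71: 7 days at every f.

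**What a hold or reduction does (dosage x f).**

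| Dosage | f = 1.5 | f = 2 | f = 3 | f = 4 |
|---|---|---|---|---|
| Held at 30 mg/day | 45 | 60 | 90 | 120 |
| Reduced to 20 mg/day | 30 | 40 | 60 | 80 |
| Reduced to 15 mg/day | 22.5 | 30 | 45 | 60 |

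A hold at 30 mg/day is enough up to f = 2 and not beyond, so permission to reduce is needed too. The lowest level suffices only up to f = 60/15 = 4; at f = 5 it gives 75.

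**Can scheduled contacts catch it?** Contacts are 14 days apart, and at most 14 + 3 + 3 = 20 days with the visit windows. A 7-day course with a random start falls wholly between nominal contacts with probability (14 - 7)/14 = 50%; a 10-day course, (14 - 10)/14 = 29%.

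**Cost of a full step-down.** Suppose dosage drops to 15 mg/day for a course of up to 14 days begun on day 15, 29, 43, 57 or 71. Then 4, 3, 2, 1 or 0 upward steps remain, and the highest dosage reachable by week 12 is 50, 40, 30, 20 or 15 mg/day.

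**Idelalisib.** Set side by side, 6.1 allows the drug with study drug continued; 6.2, if Idelasib is the same drug, requires study drug to be stopped. Both cannot be followed.

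**The case against.** The strongest defence is that monitoring was a deliberate and disclosed choice. Section 2.3 says the flexible design reflects clinical practice and tests buspirone rather than a fixed dosage, and 3.3 aims for a representative sample. Expected intolerabilities are described as not serious or reversible (2.2, 13.1). Concomitant medications and dosage are reviewed at every visit. The UKU, which covers tremor, rigidity and hypokinesia, is also given by telephone. Unscheduled visits are available on request and include the MDS-UPDRS motor examination.

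Much of this stands, and it limits the severity. It does not close the gap: these safeguards mostly act once symptoms appear, and no dosing action is tied to the medication record. Sections 2.4 and 10.1 invite calls about worsening anxiety or adverse events, not about new medicines (the consent form was not available for review).

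A reader might infer that dosage may be lowered only after an adverse event. The text does not say so. The sentence in 5.1.2 is a permission. Sections 5.1.1 and 8.2 allow adjustment as necessary and tolerated, 5.6 has the investigator consider the need for adjustment at each visit, and 2.1 and 2.3 are softer on escalation. The supportable claim is that no hold is required and no pre-emptive reduction is expressly provided for.

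It is also fair that a compulsory drop to 7.5 mg twice daily, or stop-and-restart, could do harm. Lost anxiolytic effect can lead to withdrawal (7.0), and a participant still off study drug at week 12 is a primary failure.

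**Conclusion.** The point holds as a modest dosing-safety gap with an inexpensive remedy. As written, the plan can escalate a participant who has just started a strong inhibitor or stopped an inducer, and it gives conflicting instructions on idelalisib.

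The size is uncertain. The number affected is not given and may be zero. The 28 to 70 days are illustrative upper bounds on assumed fold-changes. They also assume that effects follow parent-drug exposure; 1.3 names an active metabolite, so the equivalence may be weaker. The 60 mg/day figure is a dosage threshold from small studies, not an exposure limit.

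Three further inferences are not supported:

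- That the primary analysis is invalid. Non-completion for any reason is counted by rule, and that count stands.
- That participants on a stable interacting drug from baseline are exposed in the same way. Stepwise titration from 7.5 mg twice daily protects them.
- That grapefruit is barred in the placebo arm alone. The 5.1.2 table as extracted carries the warning only in the placebo row, but 6.2 bars grapefruit juice for everyone; at most this is clerical.

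**What to change.** 1. In 6.1, 5.1.2 and 5.6, ask participants to call before starting or stopping a listed interacting drug. When a listed inhibitor, diltiazem, verapamil or a listed macrolide is started, or a listed inducer is stopped, do not escalate while that change is under way. The sponsor should define when it is over, because the documents give no basis for a period.
2. State that the investigator may then reduce study drug or placebo to a lower 5.1.2 level, blinded and in both arms, without waiting for an adverse event, and re-titrate by 5.1.2 afterwards. Do not mandate 7.5 mg twice daily or stop-and-restart. No new rule is needed for starting nefazodone.
3. Keep idelalisib in 6.2 only, correctly spelled, as the conservative choice, and delete it from 6.1.
4. In 13.2, which already counts dosage reductions, show pre-emptive reductions separately from those for adverse events, descriptively by arm. Exclude nobody and add no test.

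**Cost.** Affected participants may spend time at a lower dosage and not regain 30 mg twice daily by week 12. Completion could shift slightly either way, by at most one failure per affected participant: an adverse-event stop avoided, or a withdrawal for worsening anxiety added. A reduction may need an unscheduled visit, with the examinations in 5.2.5, and an extra dispensation through the unblinded coordinator (8.4). The text changes amount to a short paragraph, one drug name and one split of an existing count.
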